5.5 Study Enrollment Exclusion Criteria

In addition to the procurement exclusion, subjects (both with Vigil manufactured and undergoing procurement) will NOT be eligible for study registration and enrollment if meeting any of the following criteria:

- 1. Participation in another clinical study with an investigational product within the last 3 weeks prior to study start.
- 2. Receipt of steroid therapy within the 2 weeks of the first dose of study therapy.
- Live vaccine used for the prevention of infectious disease administered < 30 days prior to the start of study therapy. NOTE: Subjects, if enrolled, should not receive live vaccine during the study and for 5 months after the last dose of atezolizumab.
- 4. Post-surgery complication that in the opinion of the treating investigator would interfere with the subject's study participation or make it not in the best interest of the subject to participate.
- 5. Mean QT interval corrected for heart rate (QTc) ≥470 ms calculated from 3 electrocardiograms (ECGs) using Fridericia's Correction.
- 6. Female subjects who are pregnant, breast-feeding or of reproductive potential who are not employing an effective method of birth control defined in the protocol. Effective contraception is required for women receiving atezolizumab for 5 months after the last dose.

- 7. Any condition that, in the opinion of the investigator, would interfere with evaluation of study treatment or interpretation of patient safety or study results.
- 8. Receipt of the last dose of anti-cancer therapy (chemotherapy, immunotherapy, endocrine therapy, targeted therapy, biologic therapy, tumor embolization, monoclonal antibodies, other investigational agent) less than 21 days prior to the first dose of study drug or less than 6 weeks for nitrosourea or mitomycin C.
- 9. Receipt of any anti-cancer therapy between tissue procurement on CL-PTL-126 and first dose of study drug.

Patients should continue the combination of Vigil with atezolizumab until disease progression is documented, or toxicity supervenes. Depending on the number of doses of Vigil manufactured, it is expected that 4 to12 doses of Vigil will be administered. Once Vigil doses are exhausted, subjects whose disease is stable or responding, may continue to receive single agent atezolizumab until disease progression.

5.6 Withdrawal from Study Treatment

Subjects will be taken off study treatment if any of the following occur:

- 1. An AE that, in the opinion of the Investigator or the Sponsor, contraindicates further dosing.
- 2. Patients with disease progression assessed by RECIST 1.1 criteria as determined by the investigator will not receive further Vigil or atezolizumab treatment.
- 3. The patient experiences unacceptable (≥Grade 3) toxicity felt to be related to treatment with Vigil, atezolizumab, or study related procedure that persists for >2 weeks.
- 4. Persisting Grade 3 or 4 toxicity unrelated to treatment, defined as failing to normalize within 4 weeks.
- 5. \geq Grade 3 allergic reactions related to Vigil or atezolizumab.
- 6. Grade 2 autoimmune reactions unless there is evidence of clinical benefit.
- 7. ≥ Grade 3 autoimmune reactions.
- 8. An intercurrent illness, which would in the judgment of the investigator, affects assessments of clinical status to a significant degree or requires discontinuation of study treatment.
- 9. Non-protocol therapy is administered during study treatment.
- 10. Non-compliant with protocol or treatment.
- 11. Patient refuses to continue treatment.
- 12. Sponsor discontinuation of the protocol.

The date of and reason for discontinuation must be noted in the subject's source document. Every effort should be made to complete the appropriate assessments.

At any time, subjects are free to discontinue Vigil and/or atezolizumab without prejudice to further treatment. A subject who decides to discontinue Vigil and/or atezolizumab will always be asked about the reason(s) for discontinuation and the presence of any AE. If possible, they will be seen and assessed by an Investigator. Adverse events will be recorded from time of first dose of Vigil and/or atezolizumab, throughout the treatment period and including the follow-up period:

- 30 days following the last study treatment or until another therapy has been initiated, whichever is earlier, regardless of causality.
- SAEs and AESIs are to be followed for 30 days after the last dose of study drug or the initiation of new therapy, whichever is earlier.

The Study Physician should be notified of any ongoing AE that may delay treatment or necessitate permanent discontinuation of treatment.

The date of and reason for discontinuation must be noted in the electronic Case Report Form (CRF). Every effort should be made to complete the appropriate assessments.

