6.2.2 Dose Reduction / Escalation

Dose reduction or dose increase is not allowed for Vigil or atezolizumab.

Dose Holding Criteria

Both atezolizumab and Vigil should be held for any of the following AEs. Cycles held for toxicity should be made up (that cycle number is delayed rather than skipped). Atezolizumab and Vigil held may be resumed in patients whose AEs recover to Grade 0-1, with the exception of rash, which should recover to Grade 2 or better.

- Grade 2 pneumonitis
- Aspartate aminotransferase (AST) or alanine aminotransferase (ALT) greater than 3 and up to 5 times upper limit of normal (ULN) or total bilirubin greater than 1.5 and up to 3 times ULN
- Grade 2 or 3 diarrhea or colitis
- Symptomatic hypophysitis, adrenal insufficiency, hypothyroidism, hyperthyroidism, or Grade 3 or 4 hyperglycemia
- Grade 2 ocular inflammatory toxicity
- Grade 2 or 3 pancreatitis, or Grade 3 or 4 increases in amylase or lipase levels (greater than 2.0 times ULN)
- Grade 3 or 4 infection
- Grade 2 infusion-related reactions
- Grade 3 rash
- Grade 2 nephritis

Based on the mechanism of action of atezolizumab leading to T-cell activation and proliferation, there is the possibility of observing immune related Adverse Events (irAEs) during the conduct of this study. Potential irAEs include immune related colitis, pneumonitis, hepatitis, and endocrinopathies. Subjects should be monitored for signs and symptoms of irAEs. Subjects should be monitored for signs and symptoms of irAEs. In the absence of an alternate etiology (e.g., infection or PD) signs or symptoms of colitis, pneumonitis, hepatitis, and endocrinopathy should be considered to be immune-related.

Study Regimen Delay

- Cycles held for toxicity should be made up and not deleted.
- Dosing of atezolizumab and Vigil may be restarted when toxicity is ≤ Grade 1 severity with the exception of rash which may be ≤ Grade 2.
- In case of immune related adverse events, treatment with atezolizumab and Vigil may be delayed for up to 15 weeks (12 weeks for steroid therapy plus 3 weeks for gradual steroid tapering to a dose of ≤ 10 mg/day of prednisone.
- Subjects who delay treatment for more than 15 weeks due to toxicities will be considered off study treatment (see Section 6.3 Withdrawal).

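### Sections 5.6 and 6.2.2 prescribe different actions for some of the same Grade 2 and 3 immune-related events, and the protocol does not say which applies

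*Combined protocol and SAP*

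**What the plan says.** Section 5.6 (Withdrawal from Study Treatment) is mandatory, and one item is enough: "Subjects will be taken off study treatment if any of the following occur". Three items matter here.

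- Item 3: Grade 3 or higher "toxicity felt to be related to treatment with Vigil, atezolizumab, or study related procedure that persists for >2 weeks".
- Item 6: "Grade 2 autoimmune reactions unless there is evidence of clinical benefit".
- Item 7: "Grade 3 autoimmune reactions" or worse, with no exception and no waiting time.

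Section 6.2.2 (Dose Reduction / Escalation) sets out holding: "Both atezolizumab and Vigil should be held for any of the following AEs". Its list includes "Grade 2 or 3 diarrhea or colitis", Grade 2 or 3 pancreatitis, Grade 3 rash, and Grade 2 pneumonitis, nephritis and ocular inflammatory toxicity. On recovery, "Atezolizumab and Vigil held may be resumed in patients whose AEs recover to Grade 0-1", with rash allowed at Grade 2 or better. For immune-related events the delay may last up to 15 weeks, made up of 12 weeks of steroid therapy and 3 of taper. After that, "Subjects who delay treatment for more than 15 weeks due to toxicities will be considered off study treatment".

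Three further passages bear on how the rules fit together. Section 6.2.2 presumes colitis, pneumonitis, hepatitis and endocrinopathy to be immune-related when there is no other cause. It also has a separate list of events for which atezolizumab stops permanently. Section 6.2.1 lets treatment continue unless, among other things, a 5.6 criterion is met.

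**The concern.** The two sections read as if they were written separately. A site facing an immune-related event can find it in both and obtain a different instruction from each. One site may re-dose a subject whom 5.6 removes. Another may stop a subject whom 6.2.2 would allow to resume. Either action departs from one section of the protocol.

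The primary objective is the tolerability and safety of the combination, so three things are at stake: the subject's safety, the exposure received, and the reason for discontinuation, which 5.6 requires on the CRF. In Part 2, a subject taken off during the two single-agent cycles never receives the combination.

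**Working it through.** The only figure to reproduce is the delay limit: 12 + 3 = 15 weeks, which agrees with Section 6.2.2 and equals 15 / 3 = 5 cycles of 21 days. The rest is a comparison of the rules, event by event.

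| Event | Section 5.6 | Section 6.2.2 | Result |
|---|---|---|---|
| Immune-related Grade 3 colitis | Off treatment (item 7) | Hold; may resume at Grade 0-1, unless the atezolizumab discontinuation features are met | Conflict, outside those features |
| Grade 3 pancreatitis, if judged autoimmune | Off treatment (item 7) | Hold; may resume at Grade 0-1 | Conflict |
| Grade 3 rash, if judged autoimmune | Off treatment (item 7) | Hold; may resume at Grade 2 or better | Conflict |
| Immune-related Grade 2 pneumonitis or colitis, no evidence of clinical benefit | Off treatment (item 6) | Hold; may resume, no benefit condition | Conflict |
| Grade 2 nephritis or ocular inflammation, if judged autoimmune, no evidence of clinical benefit | Off treatment (item 6) | Hold; may resume, no benefit condition | Conflict |
| The same Grade 2 events with evidence of clinical benefit | Not removed by item 6 | Hold; may resume | No conflict |
| Grade 3 pneumonitis, nephritis or ocular toxicity, if judged autoimmune | Off treatment (item 7) | Atezolizumab permanently stopped | No conflict over atezolizumab |

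**Time limits.** Item 3 measures how long toxicity persists at Grade 3 or higher. The 15-week limit measures how long dosing is delayed. If the event falls below Grade 3 within 2 weeks and a long steroid taper follows, neither limit is broken. They disagree only when related immune toxicity itself remains at Grade 3 or higher for more than 2 and up to 15 weeks. If both clocks are taken to start together, that window is 15 - 2 = 13 weeks. Section 6.2.2 also stops atezolizumab for any Grade 4 event, so for that drug the window is in effect a Grade 3 one.

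**Is there a rule of precedence?** Section 6.2.1 keeps 5.6 in force during dosing but does not say how the resumption rule in 6.2.2 gives way. The 15-week rule refers the reader to a withdrawal section numbered 6.3. Section 6.3 is Toxicity; withdrawal is 5.6, which contains no 15-week limit.

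**Are these the same events?** Section 5.6 says *autoimmune* and 6.2.2 says *immune related*. The protocol does not distinguish the terms. The 6.2.2 presumption of immune cause covers colitis and pneumonitis directly, so those two are stated above without the qualifier used for pancreatitis, rash, nephritis and ocular events.

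**The case against.** The best defence is that 6.2.2 operates inside 5.6. Section 5.6 is mandatory, the resumption wording is permissive, and 6.2.1 makes continued treatment subject to 5.6. This is an ordinary reading, and some sites would adopt it. It does not settle the matter. If 5.6 always controlled, the permission to resume would be void for immune-related Grade 3 colitis, which 6.2.2 expressly puts on its hold list.

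A second defence is that *autoimmune reactions* may mean something narrower than immune-related events. That is possible, but nothing in the protocol says so, and the item 3 conflict does not depend on the term.

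A third is central contact. The Study Physician is told of events that may delay or stop treatment, the Medical Monitor takes questions about immune-related events, and adverse events of special interest are reported within 24 hours. These steps reduce divergence between sites but do not supply a written rule.

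Several stronger readings are tempting, and the documents do not support them.

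- A reader might express 2 against 15 weeks as a ratio. The clocks measure different things, so a ratio has no meaning.
- A reader might count nearly the whole hold list as conflicting. The presumption of immune cause names four events only. The liver entry consists of laboratory thresholds, and the symptomatic endocrine events carry no grade that would place them under item 6 or 7.
- A reader might argue that a Grade 2 event in the Part 2 lead-in comes before any scan could show benefit. Item 6 does not limit benefit to imaging. Appendix B has ECOG status at every treatment cycle and CA-125 when records provide it, and Section 6.4 judges continued treatment partly on symptoms and ECOG.
- A reader might assume that every Grade 3 colitis case is resumable under 6.2.2. That section itself stops atezolizumab permanently for diarrhea with certain severe features.

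**Conclusion.** The point holds for a defined set of events. Items 6 and 7 of 5.6 conflict with the hold-and-resume rule for immune-related Grade 3 colitis outside the discontinuation features, and for Grade 2 pneumonitis or colitis without evidence of clinical benefit. The same applies to Grade 3 pancreatitis or rash, and to Grade 2 nephritis or ocular inflammation without such benefit, where these are judged autoimmune. Item 3 conflicts with the permitted delay only in the window described above.

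The conclusion assumes that *autoimmune* and *immune-related* overlap, as the absence of any distinction suggests. If they were meant to differ, the item 3 conflict would remain and the missing definition would be the fault to correct.

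The effect on results cannot be put in numbers. A reader might infer a shift of some percentage points in a toxicity-discontinuation rate, but Section 16.1 defines no such rate; it summarises adverse events by grade, system organ class and preferred term. The condition for opening Part 2 is also untouched, since it rests on serious, unexpected toxicity in the first subject's first cycle. What is affected is the handling of individual subjects, their exposure, and the consistency of recorded discontinuation reasons. In a safety study that is enough to require correction.

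**What to change.** Reconcile items 3, 6 and 7 of Section 5.6 with Section 6.2.1 and with the hold, resume, delay and permanent-discontinuation rules of 6.2.2, so that each event and grade leads to one action and one time limit. State when each clock starts. State whether *autoimmune* and *immune-related* mean the same. Correct the cross-reference in the 15-week rule from 6.3 to 5.6. Record reasons for discontinuation on the CRF under the reconciled rule. Which rule prevails is for the sponsor's clinical team, and this review takes no position on it.

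The cost is protocol amendment wording and a notice to sites, with no additional subjects or procedures.

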6.0 INVESTIGATIONAL PLAN

6.1 Subject Screening and Registration

Written documentation of full, unconditional IRB approval of the protocol and consent document must be on file before a subject can be screened. Study participation begins once written informed consent is obtained.

The Research Nurse or Clinical Research Coordinator will register the subject via email addressed to the Sponsor.

Please allow 48 hours for subject registration as the subject's source documents will be reviewed to ensure they meet the inclusion/exclusion criteria. Once confirmed, the site will be notified of eligibility by the Sponsor.

6.2 Study Treatment Administration

Treatment will be administered on an outpatient basis.

6.2.1 Schedule, Dose and Administration

Subjects will receive Vigil and atezolizumab according to the schedule outlined in Appendix B.

A study cycle is defined as 21 days (3 weeks).

Vigil immunotherapy will be administered at a concentration of 1×10^6 or 1×10^7 cells/dose given via intradermal injection every 3 weeks for a minimum of 4 doses and a maximum of 12 doses.

Atezolizumab will be administered at the FDA approved dose and schedule as described in the U.S. Package Insert (USPI). Thus, atezolizumab is to be administered at a dose of 1200 mg as an intravenous infusion every 3 weeks. The initial dose is to be administered over one hour and if well tolerated, subsequent infusions may be administered over 30 minutes.

The sites of injection for Vigil will be rotated between the right and left upper arms. If the ipsilateral axillary lymph nodes were radiated or surgically removed during prior therapy, alternative sites will be used. Subjects receiving Vigil will be observed for at least 30 minutes following administration.

Investigational treatment may continue unless documented disease progression, discontinuation for toxicity, withdrawal of consent, or meeting other criteria for withdrawal from study detailed in Section 5.6.

6.2.2 Dose Reduction / Escalation

Dose reduction or dose increase is not allowed for Vigil or atezolizumab.

Dose Holding Criteria

Both atezolizumab and Vigil should be held for any of the following AEs. Cycles held for toxicity should be made up (that cycle number is delayed rather than skipped). Atezolizumab and Vigil held may be resumed in patients whose AEs recover to Grade 0-1, with the exception of rash, which should recover to Grade 2 or better.

- Grade 2 pneumonitis
- Aspartate aminotransferase (AST) or alanine aminotransferase (ALT) greater than 3 and up to 5 times upper limit of normal (ULN) or total bilirubin greater than 1.5 and up to 3 times ULN
- Grade 2 or 3 diarrhea or colitis
- Symptomatic hypophysitis, adrenal insufficiency, hypothyroidism, hyperthyroidism, or Grade 3 or 4 hyperglycemia
- Grade 2 ocular inflammatory toxicity
- Grade 2 or 3 pancreatitis, or Grade 3 or 4 increases in amylase or lipase levels (greater than 2.0 times ULN)
- Grade 3 or 4 infection
- Grade 2 infusion-related reactions
- Grade 3 rash
- Grade 2 nephritis

Based on the mechanism of action of atezolizumab leading to T-cell activation and proliferation, there is the possibility of observing immune related Adverse Events (irAEs) during the conduct of this study. Potential irAEs include immune related colitis, pneumonitis, hepatitis, and endocrinopathies. Subjects should be monitored for signs and symptoms of irAEs. Subjects should be monitored for signs and symptoms of irAEs. In the absence of an alternate etiology (e.g., infection or PD) signs or symptoms of colitis, pneumonitis, hepatitis, and endocrinopathy should be considered to be immune-related.

Study Regimen Delay

- Cycles held for toxicity should be made up and not deleted.
- Dosing of atezolizumab and Vigil may be restarted when toxicity is ≤ Grade 1 severity with the exception of rash which may be ≤ Grade 2.
- In case of immune related adverse events, treatment with atezolizumab and Vigil may be delayed for up to 15 weeks (12 weeks for steroid therapy plus 3 weeks for gradual steroid tapering to a dose of ≤ 10 mg/day of prednisone.
- Subjects who delay treatment for more than 15 weeks due to toxicities will be considered off study treatment (see Section 6.3 Withdrawal).
- Treatment delay not related to toxic events (including subjects unable to adhere to dose schedule) may not extend for more than three days unless due to symptoms related to disease or infection in which case up to a 4-week delay is allowed.
- If ≥ one 2-week delay due to disease or infection occurs, subject status must be reviewed by sponsor.

Atezolizumab should be permanently discontinued for any of the following AEs:

- Any life-threatening or Grade 4 AE
- Grade 3 or 4 pneumonitis
- Aspartate aminotransferase (AST) or alanine aminotransferase (ALT) >5 times upper limit of normal or total bilirubin >3 times upper limit of normal
- Diarrhea with abdominal pain, fever, ileus, or peritoneal signs; increase in stool frequency (Grade 4) stool incontinence, need for intravenous hydration for more than 24 hours, gastrointestinal hemorrhage, and gastrointestinal perforation
- Grade 4 hypophysitis
- Myasthenic syndrome/myasthenia gravis, Guillain-Barré or meningoencephalitis (all grades)
- Grade 3 or 4 ocular inflammatory toxicity
- Grade 4 or any grade of recurrent pancreatitis
- Grade 3 or 4 infusion-related reactions
- Grade 4 rash
- Grade 3 or 4 nephritis
- Myocarditis (all grades)

For combination treatment, the occurrence of a Grade 3 or 4 toxicity attributed to Vigil will result in the cessation of Vigil dosing and continuation of single agent atezolizumab only.

Please reference https://www.gene.com/download/pdf/tecentrig_prescribing.pdf for full prescribing information regarding atezolizumab.

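### Section 6.2.2 gives conflicting actions on atezolizumab for the same Grade 4 event, and nothing in the documents ranks the rules within that section

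*Combined protocol and SAP*

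**What the plan says.** Section 6.2.2 contains three sets of rules on toxicity.

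- **Hold list** (Dose Holding Criteria). The lead-in is "Both atezolizumab and Vigil should be held for any of the following AEs", followed by "Atezolizumab and Vigil held may be resumed in patients whose AEs recover to Grade 0-1", with a separate threshold for rash. Its entries include "Symptomatic hypophysitis, adrenal insufficiency, hypothyroidism, hyperthyroidism, or Grade 3 or 4 hyperglycemia" and "Grade 3 or 4 infection", and one entry covers Grade 3 or 4 rises in amylase or lipase.
- **Stop list.** The lead-in is "Atezolizumab should be permanently discontinued for any of the following AEs". The first entry is "Any life-threatening or Grade 4 AE", without qualification by event or cause. The list names atezolizumab only, not Vigil.
- **Vigil-attribution rule.** After the stop list, for combination treatment, a "Grade 3 or 4 toxicity attributed to Vigil will result in the cessation of Vigil dosing and continuation of single agent atezolizumab only". The same sentence appears under Part 2 in the Synopsis and in Section 4.0.

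Two other sections bear on the matter. Section 5.6 item 5 takes a subject off study treatment for an allergic reaction of Grade 3 or higher related to either agent. Section 6.2.1 lets treatment continue unless, among other things, a withdrawal criterion in 5.6 is met.

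**The concern.** The primary objective (Section 3.1) is the tolerability and safety of the combination, and these are the working instructions for its most severe toxicities. If two rules in one section give different answers on re-exposure after a Grade 4 event, two sites can each follow a written rule and do opposite things: one resumes or continues atezolizumab, the other ends it permanently. The protocol would then not define how the combination is managed at the point where its safety is tested hardest.

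**Working it through.** No formula or planned figure is involved. The check lists each trigger in 6.2.2, finds those that fall under more than one rule, compares the actions on atezolizumab, and looks for text that ranks the rules.

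**Counts.** The hold list has 10 entries, of which 3 name Grade 4 (hyperglycemia; amylase or lipase; infection). The stop list has 12 entries. Of the 11 after the first, 8 name Grade 4 for a particular event (pneumonitis, diarrhea, hypophysitis, ocular toxicity, pancreatitis, infusion-related reactions, rash, nephritis), 2 apply at all grades, and 1 uses laboratory thresholds: 8 + 2 + 1 = 11. None of the 11 names hyperglycemia, infection, or amylase or lipase.

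**Side by side, action on atezolizumab:**

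| Trigger | Hold list | First stop entry | Vigil-attribution rule |
|---|---|---|---|
| Grade 4 hyperglycemia | Hold, may resume | Permanent stop | Does not apply unless attributed to Vigil |
| Grade 4 amylase or lipase increase | Hold, may resume | Permanent stop | Does not apply unless attributed to Vigil |
| Grade 4 infection | Hold, may resume | Permanent stop | Does not apply unless attributed to Vigil |
| Any Grade 4 toxicity attributed to Vigil | Only if the event is listed | Permanent stop | Continue |

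All 3 hold entries that name Grade 4 therefore clash with the first stop entry, whatever the cause. The attribution rule adds a second clash. The two meet in one case: Section 14.4 lists hyperglycemia among expected Vigil events, so Grade 4 hyperglycemia attributed to Vigil attracts three actions on atezolizumab (hold, stop, continue).

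The endocrine terms that share the hyperglycemia entry carry no grade. They could overlap too, but are not counted because the hold list does not name Grade 4 for them.

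**Does a normal reading settle it?** Two readings are available, and they give opposite answers.

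- *Specific over general.* Elsewhere the lists mostly join without overlap: nephritis is held at Grade 2 and stopped at Grade 3 or 4; rash is held at Grade 3 and stopped at Grade 4. The event-by-event stop entries would be largely redundant if the first entry already covered every Grade 4 event. This reading narrows a first entry that states no exception.
- *Stricter rule prevails.* This takes the first entry at its word. It then removes the resumption that the hold list gives atezolizumab for three Grade 4 events, although that sentence names both agents.

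The protocol writes down neither reading.

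**Search for a ranking.** Section 6.2.1 points to 5.6 but says nothing about the order of rules inside 6.2.2. The Synopsis and Section 4.0 refer atezolizumab-related safety events to the US package insert, and 6.2.2 points to the prescribing information. None of these says whether the insert overrides 6.2.2, and its content is not in the documents.

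**The case against.** **Resumption is only permitted, not required.** A site that holds and then stops permanently breaches neither list. That is correct, but a site that resumes, as the hold list allows, breaches the stop list. Nor does the argument reach the attribution rule, which directs continuation.

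**The attribution rule reads as a specific exception.** It follows the list, is confined to combination treatment, and uses firmer wording than the stop list. This is a reasonable reading, but it is not written, and the first stop entry contains no carve-out by cause.

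**The sponsor is informed.** Section 5.6 has the Study Physician notified of ongoing events that may delay or end treatment. Life-threatening events are serious under Section 14.0 and reach the sponsor within 24 hours under Section 14.6. Under 5.6 item 1 the investigator or sponsor may stop dosing. These routes make uncoordinated action less likely. They yield case-by-case decisions and do not state the rule.

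**Stronger readings that the documents do not support:**

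- A reader might infer that the protocol has no order of precedence at all. Section 6.2.1 makes continued treatment subject to 5.6, so the gap is established only within 6.2.2.
- A reader might treat 5.6 item 5 as a third firm contradiction, because the attribution rule would continue atezolizumab after a Grade 3 or higher allergic reaction related to Vigil. That follows only if study treatment in 5.6 means both agents, which 5.6 does not say. Even then, 6.2.1 may already give 5.6 priority.
- A reader might take the wrong cross-reference in 6.2.2 (withdrawal placed in 6.3, which is Toxicity) as evidence on precedence. It concerns only delays beyond 15 weeks and is editorial.

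**Conclusion.** The point holds: Section 6.2.2 is wrong as written. Its size is two conflicts on atezolizumab. The first covers three named Grade 4 events and needs no assumption about cause. The second covers any Grade 4 toxicity attributed to Vigil. The clash with 5.6 item 5 is conditional, as set out above.

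No conflict is claimed for Vigil between the hold and stop lists, because the stop list does not name it. No frequency is estimated. Section 1.4 reports no Grade 3 or 4 events attributed to Vigil in over 160 patients, so the second conflict may arise rarely, but that experience is not described as combination treatment.

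A reader might infer bias in the safety or efficacy results. The documents do not support that: Section 16.1 summarizes adverse events by grade, class and relatedness, and no effect on a planned endpoint is claimed. The harm is that the action after a Grade 4 event is not defined in a trial whose primary objective is safety.

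**What to change.** In one amendment:

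1. Reconcile the hold list, the stop list and the Vigil-attribution rule in 6.2.2, with the repeats under Part 2 in the Synopsis and Section 4.0, so that each event and grade has one action for each agent.
2. State whether the first stop entry has exceptions for hold-list events and for toxicity attributed to Vigil.
3. State in 5.6 whether study treatment means both agents or only the causal one, and whether 5.6 or 6.2.2 governs when both apply.
4. As an editorial item, correct the withdrawal cross-reference in 6.2.2 from 6.3 to 5.6.

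Which action is right for each event is for the sponsor's medical team to decide; no view is taken here.

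The cost is a formal amendment with sponsor and IRB/IEC approval under Section 7.5. It adds no procedures, visits or patients.
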